4.2.3 Replacement

Dropout patients will need to be replaced.

Patients will be considered inevaluable for the primary endpoint of 6 month of OS if they are not able to complete first cycle. Inevaluable patients will be replaced

5. Treatment[s]

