4.2 Withdrawal of subjects from study

4.2.1 Withdrawal

Subjects **must be withdrawn from the trial** (treatment and procedures) for the following reasons:

- Subject withdraws consent from study treatment and study procedures. A subject must be removed from the trial at his/her own request or at the request of his/her legally acceptable representative. At any time during the trial and without giving reasons, a subject may decline to participate further. The subject will not suffer any disadvantage as a result.
- Pregnancy. Pregnancy will be reported as an SAE. (Note: subjects who have been withdrawn from treatment with study drug because of pregnancy should not undergo CT scans [with contrast]/MRI or bone scans while pregnant.)
- If, in the investigator's opinion, continuation of the trial would be harmful to the subject's well-being.
- Subject is lost to follow-up.
- Progression of disease
- Death.

Subjects **may be** withdrawn from the study for the following reasons:

- The subject is non-compliant with study drug, trial procedures, or both; including the use of anti-cancer therapy not prescribed by the study protocol.

- Severe allergic reaction to regorafenib (such as exfoliative erythroderma or Grade 3 or 4 hypersensitivity reaction).
- The development of a second cancer.
- Development of an intercurrent illness or situation which would, in the judgment of the investigator, significantly affect assessments of clinical status and trial endpoints.
- Deterioration of ECOG performance status to 3 or 4.
- Use of illicit drugs or other substances that may, in the opinion of the investigator, have a reasonable chance of contributing to toxicity or otherwise skewing trial result.

Any subject removed from the trial will remain under medical supervision until discharge or transfer is medically acceptable.

In all cases, the reason for withdrawal must be recorded in the CRF and in the subject's medical records.

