4.2.2 Screen Failures/Dropouts

A subject who discontinues study participation prematurely for any reasons except death, disease progression and severe toxicity is defined as a dropout.

A subject who, for any reason (e.g. failure to satisfy the selection criteria), terminates the study before the time point used for the definition of “dropout” (see above) is regarded a “screening failure”.

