8.1 Sample Size Determination

Overall Survival (OS) at 6 month is the primary endpoint on this study. OS is defined in section 8.2. Dropouts/screen failures defined in section 4.2.2 and those who are lost

follow-up prior to 6 months from starting on trial except death are not evaluable for the primary endpoint, and they will be replaced by new patients. The study will test the null hypothesis of $\leq 30\%$ of OS at 6 month against the alternative of $\geq 50\%$ of OS at 6 month (HR = 0.578 under exponential model). The sample size was determined, based on the Simon's two-stage minimax design. With one-sided 10% of type I error rate and 90% statistical power, a sample of evaluable 39 will be evaluated: 28 in first stage and additional 11 in second stage. If 8 or more out of 28 survive 6 months or more, the study goes on the second stage.. REGORAFENIB will be deemed to have good activity if ≥ 16 out of 39 patients survive 6 months or more from starting on trial. The continuation of accrual may be allowed while the analysis for early stopping being conducted. We expect to accrue 2 or more patients per month among 6-7 participating institutions and will follow up patients 6 months or more.

Dropouts/screen failures defined in section 4.2.2 and those who are lost follow-up prior to 6 months from starting on trial except death, disease and severe toxicity are not evaluable for the primary endpoint, and they will be replaced by new patients

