8.2 Statistical Analysis

Overall survival (OS) is defined as the time from starting on trial to date of death due to any cause and progression-free survival (PFS) is defined as the duration of time from start of treatment to time of progression or death, whichever comes first. The final analysis will be conducted after the follow-time of the last patient exceeds 6 months. The primary endpoint of the study is OS at 6 month. The experimental treatment will be deemed to have good activity if ≥ 16 out of 39 evaluable patients survive 6 months or more. OS will be estimated using the Kaplan-Meier method and the two-sided 95% confidence interval (CI) for median OS will be computed using log-log transformation.

The secondary endpoints in this study include the disease control response (DCR) defined as (CR + PR+ SD), toxicity, and PFS. DCR rate will be reported with 95% CI computed by the Clopper-Pearson method. The frequency and severity of adverse events and tolerability of the regimen will be summarized using descriptive statistics. PFS with 95% CI will be estimated. As exploratory objective, the association between biomarkers and clinical outcomes (DCR rate, OS and PFS) will be examined using multiple logistic regression and the multivariable Cox regression model. A p-value of < 0.05 will be considered statistically significant. Frequency and severity of adverse events will be summarized using descriptive statistics.

9. Safety Monitoring

Safety assessments will consist of monitoring and recording all adverse events and serious adverse events, the regular monitoring of hematology and blood chemistry parameters and regular physical examinations. Adverse events will be evaluated continuously throughout the study. Safety and tolerability will be assessed according to the NIH/NCI Common Terminology Criteria for Adverse Events version 4.0 (CTCAE v4.0) that is available at:

<http://evs.nci.nih.gov/ftp1/CTCAE/About.html>

The PMC monitors its assigned ongoing research protocols for: adverse event reporting, data and safety monitoring, and internal audit findings. The PMC, upon review of any

agenda item, may approve the study for continuation, require revisions, suspend or close a protocol.

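### Section 4.2.3 removes and replaces patients who cannot complete cycle 1, deaths included, which is inconsistent with Section 8.1; if followed, it tilts the 8/28 and 16/39 counts toward declaring activity

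*Combined protocol and SAP*

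**What the plan says.** Four places in the combined protocol and SAP decide who enters the primary count.

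- **Section 4.2.3.** It first deals with dropouts: "Dropout patients will need to be replaced". It then adds a separate rule: "Patients will be considered inevaluable for the primary endpoint of 6 month of OS if they are not able to complete first cycle", followed by "Inevaluable patients will be replaced". No reason for non-completion is excepted. A cycle is 28 days.
- **Section 8.1.** It states evaluability twice, with no cycle-1 criterion either time. Both statements cover dropouts and screening failures as defined in 4.2.2, and patients lost to follow-up. The first ends "follow-up prior to 6 months from starting on trial except death are not evaluable for the primary endpoint"; the second ends "except death, disease and severe toxicity are not evaluable for the primary endpoint, and they will be replaced by new patients".
- **Section 4.2.2.** "A subject who discontinues study participation prematurely for any reasons except death, disease progression and severe toxicity is defined as a dropout". Its second sentence classes a subject who leaves for whatever reason before the dropout time point as a screening failure, but no time point is given.
- **Section 8.2.** OS runs from starting on trial to death from any cause. The activity rule is at least 16 "out of 39 evaluable patients survive 6 months or more", so it depends on whichever definition of evaluable applies.

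**The concern.** A patient who starts regorafenib and dies on day 20 has a fully observed outcome: failure to survive 6 months. Under 8.1, on its natural reading, that patient counts as a failure. Under 4.2.3 the patient is removed and someone who may succeed is enrolled instead. No text ranks the two sections.

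The trial has one arm and is decided by counts, at least 8 of 28 and then at least 16 of 39, so no control arm offsets a selected denominator. The same data could meet the activity rule under one section and miss it under the other. The stage 1 futility stop is weakened in the same way.

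**Working it through.** **1. Inputs.** From Section 8.1: null 30%, alternative 50%, 28 + 11 = 39 evaluable patients, continue if at least 8/28, active if at least 16/39, one-sided type I error 10%, power 90%.

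**2. The plan's own figures.** With X1 ~ Bin(28, p) and X2 ~ Bin(11, p),

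P(active) = Σ over x from 8 to 28 of P(X1 = x) · P(X2 ≥ 16 − x).

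At p = 0.30 this is 0.0943, and P(X1 ≤ 7), the chance of stopping at stage 1, is 0.365. At p = 0.50 it is 0.9001. The stated design reproduces, with little room between 0.0943 and the 10% limit.

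**3. Does the text of 4.2.3 allow a harmless reading?** One could take the cycle-1 sentence to mean dropouts only. But the sentence before it already replaces dropouts, and 4.2.2 keeps death, progression and severe toxicity out of that term. The cycle-1 sentence therefore adds almost only the patients whom 8.1 appears to keep.

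**4. Effect on type I error if 4.2.3 is followed.** Assumption: 30% is the 6-month survival of all patients who start. Let q be the fraction excluded and s the fraction of those who would have reached 6 months. Survival among the patients counted is

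p* = (0.30 − q·s) / (1 − q).

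For example, q = 0.05 and s = 0 gives 0.30/0.95 = 0.3158; q = 0.05 and s = 0.20 gives (0.30 − 0.01)/0.95 = 0.3053. Putting p* into the formula in step 2:

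| q | p*, s = 0 | type I error | stage 1 stop | p*, s = 0.20 | type I error |
|---|---|---|---|---|---|
| 0 | 0.3000 | 0.094 | 0.365 | 0.3000 | 0.094 |
| 2% | 0.3061 | 0.110 | 0.339 | 0.3020 | 0.099 |
| 5% | 0.3158 | 0.137 | 0.299 | 0.3053 | 0.107 |
| 10% | 0.3333 | 0.196 | 0.235 | 0.3111 | 0.123 |

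The 10% limit is passed at q = 0.78% when s = 0 (0.0078 × 39 = 0.30 patients) and at q = 2.3% when s = 0.20 (0.023 × 39 = 0.90 patients). With s = 0.30, type I error stays at 0.0943 for every q. With s = 0.40 and q = 10% it falls to 0.071.

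**5. Same data, two answers.** Suppose 15 of 39 patients reach 6 months and 2 of the others died in cycle 1. If those deaths count, the rule is missed by one. If both are replaced, with 30% survival each, the count reaches 16 with probability 1 − 0.7² = 0.51.

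**6. The opposite assumption.** If 30% and 50% were set for cycle-1 completers, 4.2.3 causes no inflation. Counting a fraction q of cycle-1 deaths as failures then lowers survival to p(1 − q). At p = 0.50, power is 0.876, 0.834 or 0.744 for q = 2%, 5% or 10%.

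**The case against.** The strongest reply is that the sections can be read together. If completing cycle 1 is the unstated time point in 4.2.2, an early leaver is a screening failure. Section 8.1 makes screening failures not evaluable, and its exception for death can be read as attaching only to loss to follow-up. That reading is strained, and it would leave the bias in place instead of removing it. Part of it stands, though: a reader might infer that 8.1 as written is a clean safeguard and that choosing it settles the matter. The documents do not support that, because 8.1 imports the open-ended screening-failure clause.

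Three other inferences go further than the text.

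- A reader might infer that the reported OS curve is biased too. Section 8.2 attaches the word evaluable to the 16/39 rule; its Kaplan-Meier sentence names no restricted population. Bias is shown for the count rule only.
- A reader might apply a constant hazard at the null: 1 − exp(−(−ln 0.3/6) × 28/30.4375) = 16.9% dead by day 28, which gives type I error 0.313. The ECOG 0 or 1 and 12-week life-expectancy criteria make that an unlikely upper scenario.
- A reader might infer that every cycle-1 exclusion inflates the result. For stops due to progression or toxicity the direction depends on whether those patients survive worse than the rest.

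It is also fair to say that the entry criteria favour the low end of the table. The inconsistency itself needs no assumption about rates.

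**Conclusion.** The point holds, and it should be corrected before the primary analysis. Sections 4.2.3 and 8.1 define the primary denominator differently, 4.2.2 blurs it further, and no text resolves this. If 4.2.3 is followed, the direction is certain for cycle-1 deaths: known failures leave both counts and the rule leans toward declaring activity.

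The size is conditional. It rests on 30% describing all starters, on an exclusion rate that the documents do not give, and on the survival of those excluded. For 2% to 10% excluded, type I error runs from 0.110 to 0.196 if none would survive, and from 0.099 to 0.123 if 20% would. It is zero inflation if they survive as well as the rest, or if 30% was set for completers.

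**What to change.** 1. In 4.2.3, delete the cycle-1 evaluability sentence and "Inevaluable patients will be replaced".
2. In 4.2.2, limit screening failure to subjects who leave before the first dose of regorafenib.
3. In 8.1, replace the two differing exception lists with one rule, referred to by 4.2.3 and 8.2 and used for both 8/28 and 16/39. Suggested wording: *Every patient who starts regorafenib and dies before 6 months from any cause, including in cycle 1, is evaluable and counts as a failure. Patients who stop treatment for progression or toxicity stay in the denominator and are followed for vital status to 6 months.*
4. State which population the 30% and 50% describe.
5. Secondary: in 4.2.1 and the 6.1 footnotes, state that coming off treatment for any reason does not end vital-status follow-up to 6 months, within consent. Section 4.2.1 withdraws patients from study procedures as well as treatment, 6.1 footnote 1 ends the schedule on such a withdrawal, and footnote 2 covers only follow-up after progression. Section 8.1 does intend at least 6 months of follow-up, so this is a clarification.

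A cycle-1-completer analysis may be kept as a labelled sensitivity analysis.

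**Cost.** Wording, vital-status follow-up for patients who stop early, and a possibly less favourable OS figure. N = 39 and the cut-offs do not change. Type I error 0.094 and power 0.900 then hold on two conditions: 30% and 50% describe all patients who start, and the remaining replacement of dropouts and patients lost to follow-up is non-informative. If the rates were set for completers, the power loss in step 6 of the working is the price, which is why item 4 is needed.

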5.1 Treatments to be administered

All patients will receive regorafenib

Arm 1: Regorafenib

Agent	Dose	Route	Day	Schedule*
Regorafenib	160mg	PO	QD	21 days

One cycle = 28days

5.1.1 Regorafenib

Regorafenib tablets will be packaged in high density polyethylene bottles with a white child resistant closure and induction seal. Each bottle includes 30 tablets and a 3-gram desiccant. The bottles will have a label affixed containing study identification, product identification, and quantity of tablets. Once the drug has been received it must be kept in a secure, dry location. Study drug must be stored in its original bottle at a temperature not above 25°C (77°F).

The study drug must be exclusively used for the investigation specified in this protocol and it will only be accessible to authorized staff.

5.1.2 Dosage and administration:

Regorafenib tablets for oral administration are formulated as light pink oval shaped tablets debossed with “BAYER” on one side and “40” on the other. Each tablet contains 40 mg of regorafenib in the anhydrous state, which corresponds to 41.49 mg of regorafenib monohydrate, and the following inactive ingredients: cellulose microcrystalline, croscarmellose sodium, magnesium stearate, povidone, and colloidal silicon dioxide. The film –coating contains the following inactive ingredients: ferric oxide red, ferric oxide yellow, lecithin (soy), polyethylene glycol 3350, polyvinyl alcohol, talc, and titanium dioxide.

5.1.3 Study Treatment

Regorafenib is administered as monotherapy during the study, 160 mg qd will be administered for 3 weeks on /1 week off. One cycle is 28 days.

Four 40-mg regorafenib tables should be taken in the morning with approximately 8 fluid ounces (240 mL) of water after a low-fat (<30% fat) breakfast. Some examples of low fat breakfasts are:

- Two slices of white toast with 1 tablespoon of low-fat margarine and 1 tablespoon of jelly and 8 ounces (240 mL) of skim milk (approximately 319 calories and 8.2 g of fat).
- One cup of cereal (i.e. Special K), 8 ounces (240 mL) of skim milk, one piece of toast with jam (no butter or marmalade), apple juice, and one cup of coffee or tea (2 g fat, 17 g protein, 93 g of carbohydrate, 520 calories).

5.1.4 Dose Modification for management of adverse events

5.1.4.1 Dose Reduction Levels

The starting dose of regorafenib is 160 mg once daily. Study medication will be administered on a 3 weeks on/1week off schedule [3 weeks out of every 4].

Doses will be delayed or reduced for clinically significant hematologic and non-hematologic toxicities that are related to protocol therapy according to the guidelines shown in the Dose Delays/Dose Modifications table that follows. Dose modifications will

follow predefined dose levels. Dose adjustments for hematologic toxicity are based on the blood counts obtained in preparation for the day of treatment.

The modifications of regorafenib will follow the following predefined dose levels:		
Dose level 0 (standard starting dose)	160 mg po qd	Four 40-mg tablets of regorafenib
Dose level - 1	120 mg po qd	Three 40-mg tablets of regorafenib
Dose level - 2	80 mg po qd	Two 40-mg tablets of regorafenib

If a subject experiences more than one toxicity, dose reduction should be according to the toxicity with the highest grade

In the case of two or more toxicities of the same grade, the investigator may dose reduce according to that deemed most causally related to study treatment

If more than 2 dose reductions are required, regorafenib will be discontinued and patient will need to come off of the trial. If a dose reduction has been performed, intra-subject dose re-escalation can be considered (up to the maximal 160 mg daily dose) at the discretion of the treating physician provided that the toxicity(ies) has resolved to baseline.

The following tables outline dose adjustments for toxicities related to study drug except hand-foot skin reaction, hypertension and liver function test abnormalities.

Table 6-1: Recommended dose modification for toxicities except hand-foot-skin reaction, hypertension and ALT/ST/bilirubin			
NCI-CTCAE v4.0^a	Dose Interruption	Dose Modification^b	Dose for Subsequent Cycles
Grade 0-2	Treat on time	No change	No change
Grade 3	Delay until \leq Grade 2 ^c	Reduce by 1 dose level	If toxicity remains < Grade 2, dose re-escalation can be considered at the discretion of the treating investigator. If dose is re-escalated and toxicity (\geq Grade 3) recurs, institute permanent dose reduction.
Grade 4	Delay until \leq Grade 2 ^c	Reduce by 1 dose level. Permanent discontinuation can be considered at	

		treating investigator's discretion.	

a. NCI-CTCAE = National Cancer Institute - Common Terminology Criteria for Adverse Events, version 4.0
 
b. Excludes alopecia, non-refractory nausea/vomiting, non-refractory hypersensitivity and nonclinical and asymptomatic laboratory abnormalities.
 
c. If no recovery after a 4 week delay*, treatment should be permanently discontinued unless subject is deriving clinical benefit.
 
* Modify according to study specific cycle length
			

The table above outlines dose adjustments for hematologic and non-hematologic toxicities related to regorafenib except HFSR and hypertension.

In addition to these recommended dose modifications, subjects who develop diarrhea, mucositis, anorexia or other events predisposing to fluid loss or inadequate fluid intake should be carefully monitored and rehydrated as clinically necessary. This is in order to minimize the risk of postural hypotension and renal failure.

Table 6-2: Grading for Hand-Foot-Skin-Reaction

	Grade 1	Grade 2	Grade 3
NCI-CTCAE v4.0 Palmar-plantar erythrodysesthesia syndrome	Minimal skin changes or dermatitis (e.g., erythema, edema, or hyperkeratosis) without pain	Skin changes (e.g., peeling, blisters, bleeding, edema, or hyperkeratosis) with pain	Severe skin changes (e.g., peeling, blisters, bleeding, edema, or hyperkeratosis) with pain
Further description / examples of skin changes	Numbness, dysesthesia / paresthesia tingling, painless swelling, or erythema of the hands and/or feet	Painful erythema and swelling of the hands and/or feet	Moist desquamation, ulceration, blistering, or severe pain of the hands and/or feet
Effect on activities	Does not disrupt normal activities	Limiting instrumental activities of daily life (e.g., preparing meals, shopping for groceries or clothes, using the telephone, managing money)	Limiting self-care activities of daily life (e.g., bathing, dressing and undressing, feeding self, using the toilet, taking medications) and not bedridden
a. Palmer-plantar erythrodysesthesia syndrome is a disorder characterized by redness, marked discomfort, swelling, and tingling in the palms of hands or the soles of the feet.			

Table 6.3 Recommended dose modification for hand-foot-skin reaction^a

Grade of event (NCI-CTCAE v4.0)	Occurrence	Suggested Dose Modification
Grade 1	Any	Maintain dose level and immediately institute supportive measures for symptomatic relief
Grade 2	1 st occurrence	Consider decreasing dose by one dose level and immediately institute supportive measures. If no improvement, interrupt therapy for a minimum of 7 days, until toxicity resolves to Grade 0-1 ^{b, c}
	No improvement within 7 days or 2 nd occurrence	Interrupt therapy until toxicity resolves to Grade 0-1. ^c When resuming treatment, treat at reduced dose level ^b
	3 rd occurrence	Interrupt therapy until toxicity resolves to Grade 0-1. ^c When resuming treatment, decrease dose by one dose level. ^{b, d}
	4 th occurrence	Discontinue therapy
Grade 3	1 st occurrence	Institute supportive measures immediately. Interrupt therapy for a minimum of 7 days until toxicity resolves to Grade 0-1. ^c When resuming treatment, decrease dose by one dose level. ^{b, d}
	2 nd occurrence	Institute supportive measures immediately. Interrupt therapy for a minimum of 7 days until toxicity resolves to Grade 0-1. ^c When resuming treatment, decrease dose by one additional dose level ^{b, d}
	3 rd occurrence	Discontinue treatment permanently.

a. More conservative management is allowed if judged medically appropriate by the investigator.
 
b. If toxicity returns to Grade 0-1 after dose reduction, dose re-escalation is permitted at the discretion of the investigator if subject has completed one cycle at reduced dose without recurrence of event.
 
c. If there is no recovery after a 4-week delay, treatment with regorafenib will be discontinued permanently.
 
d. Subjects requiring > 2 dose reductions should go off protocol therapy.
 
e. The maximum daily dose is 160 mg.
		

At first occurrence of HFSR, independent of grade, prompt institution of supportive measures such as topical emollients, low potency steroids, or urea-containing creams should be administered.

Recommended prevention/management strategies for skin toxicities consistent with HFSR are summarized below:

Control of calluses

Before initiating treatment with regorafenib:

- Check condition of hands and feet.
- Suggest a manicure/pedicure, when indicated.
- Recommend pumice stone use for callus or 'rough spot' removal.

During regorafenib treatment:

- Avoid pressure points.
- Avoid items that rub, pinch or create friction.

Use of creams

- Non-urea based creams may be applied liberally.
- Keratolytic creams (e.g. urea-based creams, salicylic acid 6%) may be used sparingly and only to affected (hyperkeratotic) areas.
- Alpha hydroxyl acids (AHA) based creams may be applied liberally 2 times a day. Approximately 5% to 8% provides gentle chemical exfoliation.
- Topical analgesics (e.g. lidocaine 2%) are to be considered for pain control.
- Topical corticosteroids like clobetasol 0.05% should be considered for subjects with Grade 2 or 3 HFSR. Avoid systemic steroids.

Tender areas should be protected as follows:

- Use socks/gloves to cover moisturizing creams
- Wear well-padded footwear
- Use insole cushions or inserts (e.g. silicon, gel)
- Foot soaks with tepid water and Epsom salts

Hypertension

Hypertension is a known AE associated with regorafenib treatment. Subject will have their blood pressure measured at least weekly at the study site during the first 6 weeks of treatment. If additional blood pressure measurements are done outside the study site, and the blood pressure is > 140 mm Hg systolic or > 90 mm Hg diastolic (NCI CTCAE v4.0), then the subject must contact study personnel. The management of hypertension, including the choice of antihypertensive medication, will be performed according to local standards and to the usual practice of the investigator. Every effort should be made to control blood pressure by medical means other than study drug dose modification. If necessary, Table 6.4 outlines suggested dose reductions.

Table 6-4: Management of Treatment-Emergent Hypertension		
Grade (CTCAE v4.0)	Antihypertensive Therapy	Regorafenib Dosing
1 Prehypertension (systolic BP 120 - 139 mmHg or diastolic BP 80 - 89 mmHg)	None	
 • Continue regorafenib • Consider increasing blood pressure (BP) monitoring
2 Systolic BP 140 - 159 mmHg or diastolic BP 90 - 99 mmHg, OR Symptomatic increase by > 20 mmHg (diastolic) if previously within normal limits	
 • Treat with the aim to achieve diastolic BP \leq 90 mm Hg: • If BP previously within normal limits, start anti-hypertensive monotherapy • If patient already on anti-hypertensive medication, titrate up the dose. 	
 • Continue regorafenib • If symptomatic, hold regorafenib until symptoms resolve AND diastolic BP \leq 90 mm Hg^a. When regorafenib is restarted, continue at the same dose level.
3 Systolic BP \geq 160 mmHg or diastolic BP \geq 100 mmHg OR More than one drug or more intensive therapy than previously used indicated	
Treat with the aim to achieve diastolic BP \leq 90 mm Hg: Start anti-hypertensive medication
 
AND/OR Increase current anti-hypertensive medication
 
AND/OR Add additional anti-hypertensive medications.
	
 • Hold regorafenib until diastolic BP \leq 90 mm Hg, and if symptomatic, until symptoms resolve.^a • When regorafenib is restarted, continue at the same dose level. • If BP is not controlled with the addition of new or more intensive therapy, reduce by 1 dose level.^b • If Grade 3 hypertension recurs despite dose reduction and antihypertensive therapy, reduce another dose level.^c
4 Life-threatening consequences (eg, malignant hypertension, transient or permanent neurologic deficit, hypertensive crisis)	Per institutional guidelines	Discontinue therapy

a. Patients requiring a delay of >4 weeks should go off protocol therapy
 
b. If BP remains controlled for at least one cycle, dose re-escalation permitted per investigator's discretion.
 
c. Patients requiring >2 dose reductions should go off protocol therapy.
		

Liver Function Abnormalities

For patients with observed worsening of serum liver tests considered related to regorafenib (i.e. where no alternative cause is evident, such as post-hepatic cholestasis or disease progression), the dose modification and monitoring advice in Table 6-5 should be followed.

Regorafenib is a UGT1A1 inhibitor. Mild, indirect (unconjugated) hyperbilirubinemia may occur in patients with Gilbert's syndrome.

Alanine or aspartate aminotransferase (AST/ALT): for any grade increase in AST or ALT, the investigator needs to ensure that it is not due to biliary obstruction or the introduction of new drugs. Biliary obstruction should be ruled out by imaging if needed. If the elevation of AST or ALT is due to biliary obstruction, and the biliary obstruction is treated, the study drug may be restarted at the same dose level upon return of the AST and ALT to baseline or grade 2.

For any grade increase in bilirubin, the investigator needs to ensure that it is not due to biliary obstruction or the introduction of new drugs. Biliary obstruction should be ruled out by imaging if needed. If the elevation of bilirubin is due to biliary obstruction, and the biliary obstruction is treated, the study drug may be restarted at the same dose level upon return of the bilirubin to baseline or Grade 1.

Observed elevations	1st Occurrence	Restart	Re-occurrence
ALT and/or AST >5 X ULN (≥ G3)	If patient had Grade 0 or 1 AST or ALT increase at baseline, hold the drug until AST or ALT returns to Grade 1 or baseline. If patient had Grade 2 (asymptomatic) AST or ALT increase at baseline, continue treatment at same dose and follow AST or ALT weekly for 4 weeks. Hold	Reduce one dose level and measure serum liver tests weekly for at least 4 weeks.	Discontinue

	the drug if patient develops symptoms or if AST or ALT \geq 10 x IULN; restart treatment with one dose level reduction when AST or ALT returns to baseline AND patient is asymptomatic		
ALT and/or AST > 20 X ULN (\geq G4)	Discontinue		
Bilirubin (G=2)	If patient had a normal bilirubin at baseline, hold the drug until bilirubin returns to Grade 1 or baseline If patient had Grade 1 bilirubin at baseline, continue treatment at same dose and follow bilirubin weekly for 4 weeks. Hold the drug if patient develops symptoms or if bilirubin > 2 x ULN and AST or ALT \geq 5 x ULN Restart treatment when bilirubin returns to grade 1 or baseline and patient is asymptomatic.	Restart with one dose reduction	Discontinue
Bilirubin (G=3)	Discontinue		Discontinue
During the first 2 cycles of treatment, ALT, AST and bilirubin must be monitored every 2 weeks.			

Bilirubin and AST/ALT: for any grade increase in bilirubin AST or ALT, the investigator needs to ensure that it is not due to biliary obstruction or the introduction of new drugs. Biliary obstruction should be ruled out by imaging if needed. If the elevation of AST or ALT is due to biliary obstruction, and the biliary obstruction is treated, the study drug may be restarted at the same dose level upon return of the AST and ALT to baseline or grade 2.

